### **3.5.8 Treatment Compliance**

Only subjects who are randomized to JointStem will return on Visits 4, 5, 6, 7 and 8 (Months 1, 3, 6, 9 and 12) or at Early Termination. On the other hand, subjects who are randomized to the positive control group will only return on Visits 4, 5 and 6 (Months 1, 3 and 6) or at Early Termination.

## **3.6 Study Endpoints and Variables**

### **3.6.1 Study Endpoints**

The co-primary endpoints are:

Using the following three co-primary efficacy variables, the joint functional improvement of knee joint will be evaluated and gatekeeping procedures will be used for these three hypothesis tests.

- 1) Change of WOMAC score from baseline at Month 6 (JointStem group)
- 2) Change of VAS score from baseline at Month 6 (JointStem group)
- 3) MRI improvement evaluation at Month 6 (JointStem group)

MRI improvement evaluation will be finally analyzed through the following two steps:

- Radiologist will compare and analyze MRI results before and after the administration of IP and write a report for each subject.
- Principal Investigator will evaluate MRI results of subjects as one of three conditions (a: improvement, b: no change, c: progress) based on the radiologist's report stated above.

The secondary endpoints are:

- 1) JointStem group vs. positive control group
  - ① Change of WOMAC score from baseline at Month 6
  - ② Change of VAS score from baseline at Month 6
  - ③ Change of KOOS from baseline at Month 6
  - ④ Change of Lysholm Knee Scoring Scale from baseline at Month 6
  - ⑤ Change of IKDC from baseline at Month 6
  - ⑥ Change of RAND-36 Score from baseline at Month 6
- 2) JointStem group
  - ① Change of WOMAC score from baseline at Months 9 and 12
  - ② Change of VAS score from baseline at Months 9 and 12
  - ③ Comparison of MRI improvement evaluations between at Month 6 and at Months 12
  - ④ Change of Lysholm Knee Scoring Scale from baseline at Months 6, 9 and 12
  - ⑤ Change of KOOS from baseline at Months 6, 9 and 12
  - ⑥ Change of IKDC from baseline at Months 6, 9 and 12
  - ⑦ Change of RAND-36 Score from baseline at Months 6, 9 and 12
- 3) Incidence of adverse events and laboratory abnormalities

Exploratory Endpoint is:

All efficacy variables and the history of treatments and medications, which are measured at a long-term follow-up visit (24 months after injection) will be analyzed between treatment groups to see any long-term effects of JointStem. Also, MRI results of long-term follow-up visit will be compared to previous MRI results to see any long-term effects of JointStem.

### **3.6.2 Efficacy Variables**

- WOMAC score at Visits 3, 4, 5, 6, 7 and 8 (Baseline, M1, M3, M6, M9 and M12) or Early Termination (only if the subject is early terminated after Visit 3) or Final Follow-up Up Visit
- VAS at Visits 3, 4, 5, 6, 7 and 8 (Baseline, M1, M3, M6, M9 and M12) or Early Termination (only if the subject is early terminated after Visit 3) or Final Follow-up Up Visit
- MRI scan at Visits 1, 6 and 8 (Screening, M6 and M12) or Early Termination (only if the subject is early terminated after Visit 4) or Final Follow-up Visit
- KOOS at Visits 3, 4, 5, 6, 7 and 8 (Baseline, M1, M3, M6, M9 and M12) or Early Termination (only if the subject is early terminated after Visit 3) or Final Follow-up Up Visit
- Lysholm Knee Scoring Scale at Visits 3, 4, 5, 6, 7 and 8 (Baseline, M1, M3, M6, M9 and M12) or Early Termination (only if the subject is early terminated after Visit 3) or Final Follow-up Up Visit
- IKDC at Visits 3, 4, 5, 6, 7 and 8 (Baseline, M1, M3, M6, M9 and M12) or Early Termination (only if the subject is early terminated after Visit 3) or Final Follow-up Up Visit
- RAND-36 Score at Visits 3, 5, 6, 7 and 8 (Baseline, M3, M6, M9 and M12) or Early Termination (only if the subject is early terminated after Visit 3) or Final Follow-up Up Visit

### **3.6.3 Safety Variables**

- Hematology, serum chemistry and urinalysis at Visits 1, 3, 4, 5, 6, 7 and 8 (Screening, Baseline, M1, M3, M6, M9 and M12) or Early Termination (only if the subject is early terminated after Visit 3) or Final Follow-up Visit. See Section Appendix 1 for a complete list of laboratory tests to be done.
- ECG evaluation at Visits 1, 3, 6 and 8 (Screening, Baseline, M6 and M12) or Early Termination (only if the subject is early terminated after Visit 3) or Final Follow-up Up Visit
- Complete physical examination at Visits 1, 3, 5, 6, 7 and 8 (Screening, Baseline, M3, M6, M9 and M12) or Early Termination (only if the subject is early terminated after Visit 3) or Final Follow-up Up Visit
- Vital signs (sitting blood pressure, pulse, breathing, and temperature) and weight will be measured at all visits.
- Data regarding AEs and concomitant medications collected at all visits after randomization

### **3.6.4 Exploratory Variables**

The following procedures will be performed at 24-month visit ( $\pm 2$  month):

- WOMAC score
- VAS
- MRI scan
- KOOS
- Lysholm Knee Scoring Scale
- IKDC
- RAND-36 score
- Records of treatments and medications since the last visit

### **3.6.5 Observation and Measurements**

The rating scales used in this study are WOMAC (Western Ontario and McMaster Universities Arthritis Index), VAS (Visual Analog Scale), Lysholm Knee Scoring Scale, KOOS (Knee Injury and Osteoarthritis Outcome Score), IKDC (International Knee Documentation Committee), and RAND-36 questionnaires. All questionnaires are subject-administered and should be completed by the subjects alone at the beginning of each visit to minimize influences from other procedures to be performed at that visit. A short explanation should be given to each subject about the purpose and the necessity of these questionnaires.

## 4. STUDY PROCEDURES

### 4.1 Screening Procedures

A signed and dated Institutional Review Board (IRB) approved informed consent must be obtained before any study-specific procedures are performed. Once written informed consent has been obtained, the subject will be screened to determine eligibility and document adherence to the preliminary inclusion/exclusion criteria.

#### **Screening Visit 1 (Week -7)**

The following screening assessments/procedures must be performed and the results documented within approximately 7 weeks before Baseline visit unless otherwise indicated:

- Record demographic data (i.e., date of birth, race, height, and weight).
- Measure VAS (see Appendix 4).
- Record medical and medication history.
- Perform a complete physical examination.
- Measure vital signs (sitting blood pressure, pulse, breathing, and temperature).
- Measure 12-lead ECG.
- Collect blood and urine samples for hematology, serum chemistry, and urinalysis.
- Perform X-ray for Kellgren-Lawrence scale (see Appendix 2).
- Perform MRI to measure damaged cartilage area (Please follow the instruction separately provided by the sponsor). \* MRI may be performed the day of Visit 2 or after due to scheduling or re-scanning, as long as the results are confirmed prior to injection.

### 4.2 Treatment Period

#### **4.2.1 Visit 2 (Week -5)**

For subjects who are preliminarily eligible for this study based on screening procedures, Visit 2 will occur within approximately 2 weeks ( $\pm$  4 days) after Visit 1. During this visit, the following assessments/procedures should be performed:

[figure not shown]
- Measure vital signs (sitting blood pressure, pulse, breathing, and temperature) and weight.
- Confirm medical and medication history.
- Determine the final eligibility.
- Randomize to one of two groups (Please follow the randomization instruction separately provided by the sponsor).

Subjects who are finally eligible will then be taken to the operation room for the procedure of liposuction.

- In sterile conditions, approximately 10 – 40 mL of fat will be harvested using the syringe liposuction technique with Tumescent (or super-wet) local anesthesia (Please follow the liposuction instruction separately provided by the sponsor).
- Ship the packaging box containing the harvested syringe to Biostar SCRI designated by the sponsor (pre-labeled).
- Dispense a concomitant medication note.

#### 4.2.2 Preparation of Final Drug Product in Biostar SCRI

The following procedures for the preparation of final drug product will be performed by well-trained lab technicians at Biostar SCRI. The official package containing the final drug product (syringes) will be shipped to the clinical site.

#### 4.2.3 Visit 3 (Week 0)

Visit 3 will occur within 5 weeks after Visit 2. During this visit, the following assessments/procedures should be performed:

- The following questionnaires/procedures will be completed: WOMAC (see Appendix 3), VAS (see Appendix 4), Lysholm scale (see Appendix 5), KOOS (see Appendix 6), IKDC (see Appendix 7), and RAND-36 (see Appendix 8).
- Measure vital signs (sitting blood pressure, pulse, breathing, and temperature) and weight.
- Record any adverse event and any change in concomitant medications.

- Perform a complete physical examination.
- Measure 12-lead ECG.
- Collect blood and urine samples for hematology, serum chemistry, and urinalysis.
- Inject the final drug product into the cavity of knee joint (Please follow the intra-articular injection instruction separately provided by the sponsor).
- Dispense a concomitant medication note.

#### **4.2.4 Visit 4 (Month 1 ± 3 days)**

During this visit, the following assessments/procedures should be performed:

- The following questionnaires/procedures will be completed: WOMAC (see Appendix 3), VAS (see Appendix 4), Lysholm scale (see Appendix 5), KOOS (see Appendix 6), and IKDC (see Appendix 7).
- Measure vital signs (sitting blood pressure, pulse, breathing, and temperature) and weight.
- Record any adverse event and any change in concomitant medications.
- Collect blood and urine samples for hematology, serum chemistry, and urinalysis.
- Dispense a concomitant medication note.

#### **4.2.5 Visit 5 (Month 3 ± 1 week)**

During this visit, the following assessments/procedures should be performed:

- The following questionnaires/procedures will be completed: WOMAC (see Appendix 3), VAS (see Appendix 4), Lysholm scale (see Appendix 5), KOOS (see Appendix 6), IKDC (see Appendix 7), and RAND-36 (see Appendix 8).
- Measure vital signs (sitting blood pressure, pulse, breathing, and temperature) and weight.
- Record any adverse event and any change in concomitant medications.
- Perform a complete physical examination.
- Collect blood and urine samples for hematology, serum chemistry, and urinalysis.
- Dispense a concomitant medication note.

#### **4.2.6 Visit 6 (Months 6 ± 1 week)**

During this visit, the following assessments/procedures should be performed:

- The following questionnaires/procedures will be completed: WOMAC (see Appendix 3), VAS (see Appendix 4), Lysholm scale (see Appendix 5), KOOS (see Appendix 6), IKDC (see Appendix 7), and RAND-36 (see Appendix 8).
- Measure vital signs (sitting blood pressure, pulse, breathing, and temperature) and weight.
- Record any adverse event and any change in concomitant medications.

- Perform a complete physical examination.
- Measure 12-lead ECG.
- Collect blood and urine samples for hematology, serum chemistry, and urinalysis.
- Perform MRI measurement (Please follow the collection instruction separately provided by the sponsor).
- Dispense a concomitant medication note.

*\* After each subject completes Visit 6 (Month 6) and the data management team confirms all individual data have no issue, the individual database will be locked and the blinding will be open for the statistical analysis. Only subjects who are randomized to JointStem will be scheduled for Visits 7 and 8 (Months 9 and 12).*

#### 4.2.7 Visit 7 (Month 9 ± 1 week)

Only subjects who are randomized to JointStem group will visit the clinical site for the following assessments/procedures:

- The following questionnaires/procedures will be completed: WOMAC (see Appendix 3), VAS (see Appendix 4), Lysholm scale (see Appendix 5), KOOS (see Appendix 6), IKDC (see Appendix 7), and RAND-36 (see Appendix 8).
- Measure vital signs (sitting blood pressure, pulse, breathing, and temperature) and weight.
- Record any adverse event and any change in concomitant medications.
- Perform a complete physical examination.
- Collect blood and urine samples for hematology, serum chemistry, and urinalysis.
- Dispense a concomitant medication note.

#### 4.2.8 Visit 8 (Month 12 ± 1 week)

Only subjects who are randomized to JointStem group will visit the clinical site for the following assessments/procedures:

- The following questionnaires/procedures will be completed: WOMAC (see Appendix 3), VAS (see Appendix 4), Lysholm scale (see Appendix 5), KOOS (see Appendix 6), IKDC (see Appendix 7), and RAND-36 (see Appendix 8).
- Measure vital signs (sitting blood pressure, pulse, breathing, and temperature) and weight.
- Record any adverse event and any change in concomitant medications.
- Perform a complete physical examination.
- Measure 12-lead ECG.
- Collect blood and urine samples for hematology, serum chemistry, and urinalysis.
- Perform MRI measurement (Please follow the collection instruction separately provided by the sponsor).

#### **4.2.9 Early Termination Visit**

If a subject will drop-out the study before Visit 6 (Month 6), the clinical site will try to schedule an early termination visit (one of two types)

- 1) If a subject will drop-out the study before Visit 4 (Month 1), the following assessments and procedures should be performed for the early termination visit:
  - The following questionnaires/procedures will be completed: WOMAC (see Appendix 3), VAS (see Appendix 4), Lysholm scale (see Appendix 5), KOOS (see Appendix 6), IKDC (see Appendix 7), and RAND-36 (see Appendix 8).
  - Measure vital signs (sitting blood pressure, pulse, breathing, and temperature) and weight.
  - Record any adverse event and any change in concomitant medications.
  - Perform a complete physical examination.
  - Measure 12-lead ECG.
  - Collect blood and urine samples for hematology, serum chemistry, and urinalysis.
- 2) If a subject will drop-out the study after Visit 4 (Month 1), the following assessments and procedures should be performed for the early termination visit:
  - The following questionnaires/procedures will be completed: WOMAC (see Appendix 3), VAS (see Appendix 4), Lysholm scale (see Appendix 5), KOOS (see Appendix 6), IKDC (see Appendix 7), and RAND-36 (see Appendix 8).
  - Measure vital signs (sitting blood pressure, pulse, breathing, and temperature) and weight.
  - Record any adverse event and any change in concomitant medications.
  - Perform a complete physical examination.
  - Measure 12-lead ECG.
  - Collect blood and urine samples for hematology, serum chemistry, and urinalysis.
  - Perform MRI measurement (Please follow the collection instruction separately provided by the sponsor).

#### **4.2.10 Final Follow-Up Visit**

If a subject will discontinue follow-up after Visit 6 (Month 6), the clinical site will try to schedule the final follow-up visit to perform the following assessments and procedures:

- The following questionnaires/procedures will be completed: WOMAC (see Appendix 3), VAS (see Appendix 4), Lysholm scale (see Appendix 5), KOOS (see Appendix 6), IKDC (see Appendix 7), and RAND-36 (see Appendix 8).
- Measure vital signs (sitting blood pressure, pulse, breathing, and temperature) and weight.
- Record any adverse event and any change in concomitant medications.
- Perform a complete physical examination.
- Measure 12-lead ECG.
- Collect blood and urine samples for hematology, serum chemistry, and urinalysis.
- Perform MRI measurement (only if this final follow-up visit is conducted at least 1 month after Visit 6).

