### Schedule of Assessments

	Screen.	Harv.	Treat.	1 st Follow-up				2 nd Follow-Up		Long-term	
Blinding	N/A	Double Blinding							Open 		Follow-up
Visit	1	2	3	4	5	6	ET	7	8	N/A	
Week / Month	W-7	W-5	0	M1	M3	M6	<M6	M9	M12 or Final FU 	M24	
Informed consent	X										
Medical and Medication History	X	X									
Demographic information	X										
Complete physical examination	X		X		X	X	X 	X	X	X	
Vital signs and weight	X	X	X	X	X	X	X	X	X	X	
Hematology, serum chemistry, and urinalysis 	X		X	X	X	X	X 	X	X		
Pregnancy test 	X					X	X 		X		
HIV test for Screening	X										
12-lead ECG	X		X			X	X 		X		
X-ray	X										
Eligibility confirmation	X	X									
Randomization		X									
Liposuction		X									
Injection of final drug product			X								
AE and concomitant medication assessment			X	X	X	X	X	X	X		
Records of Treatment and Medications										X	
MRI scan 	X					X	X 		X	X	
WOMAC			X	X	X	X	X 	X	X	X	
VAS	X		X	X	X	X	X 	X	X	X	
Lysholm			X	X	X	X	X 	X	X	X	
KOOS			X	X	X	X	X 	X	X	X	
IKDC			X	X	X	X	X 	X	X	X	
Quality of Life (RAND-36)			X		X	X	X 	X	X	X	

1. See Appendix 1 for the complete list of laboratory tests
2. Serum pregnancy test is performed for all females of childbearing potential (please refer to the relevant inclusion criteria)
3. May be performed the day of Visit 2 or after due to scheduling or re-scanning.
4. Performed only if the early termination is after V3.
5. Performed only if the early termination is after V4.
6. Performed if the follow-up is discontinued after V6.
7. Only for JointStem group.

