#### Appendix 4. VAS (Visual Analogue Scale) for Pain

Site No: \_\_

Subject No: \_\_ \_\_

[figure not shown]
Subject Initials: \_\_ \_\_ \_\_

Visit (circle one): Baseline M1 M3 M6 M9 M12 ET ( / / ) Final FU ( / / )

Pain 100mm Visual Analogue Scale

Please mark on the scale below how you feel your pain rates today as the following example:

*Example:*

Marked Length (mm) \_\_\_\_\_

Study Coordinator:

Signature: \_\_\_\_\_ Date: \_\_\_\_\_

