## Appendix 9. MRI Improvement Evaluation

### MRI Improvement Evaluation Form

Protocol Number: JS-OAP2-US01

Site No.	Subject No.	Subject Initials

■ The time of Evaluation (from Baseline):

 From baseline at Month 6
 From baseline at Month 12

■ Principal Investigator's MRI Final Evaluation:

► Please select one of 3 followings for MRI result at above checked time.

	Ⓐ Improvement
<hr/>	
	Ⓑ No change
	Ⓒ Progress

■ Evaluated by:

Principal Investigator

---

Name / Signature

---

Date (DD-MMM-YYYY)

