6.2.3 MRI

- ① Comparison of MRI improvement evaluations between at Month 6 and at Months 9 and 12 (JointStem group)

MRI improvement evaluation at Month 12 compared to Month 6 will be analyzed using Bowker's test. The frequency and percentage of subjects whose final PI evaluation is

‘Improvement’ “No change” or “progress” will be calculated at Month 6 and Months 12. The p-value of Bowker’s test will be provided.

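### A JointStem subject with no Month 12 MRI can still be counted in the Month 12 versus Month 6 MRI comparison, through an early final scan or a carried-forward Month 6 rating

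*Protocol*

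**What the plan says.** Protocol 4.2.10 covers any stop after Month 6: "If a subject will discontinue follow-up after Visit 6 (Month 6), the clinical site will try to schedule the final follow-up visit". No visit window is given. The imaging instruction there is "Perform MRI measurement (only if this final follow-up visit is conducted at least 1 month after Visit 6". The Protocol's Schedule of Assessments and SAP Table 1 both put this visit under Visit 8, in a column labelled "M12 or Final FU", with the footnote "Performed if the follow-up is discontinued after V6". Visit 8 itself has a narrow window in Protocol 4.2.8: "Visit 8 (Month 12 ± 1 week".

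The MRI form in Appendix 9 offers two time points, Month 6 and "From baseline at Month 12". The questionnaire forms in Appendices 4 to 8 have a separate, dated choice for the final follow-up; the VAS form, for example, reads "Visit (circle one): Baseline M1 M3 M6 M9 M12 ET ( / / ) Final FU".

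On analysis, SAP 6.2.3 states "MRI improvement evaluation at Month 12 compared to Month 6 will be analyzed using" Bowker's test, and adds the frequency and percentage in each rating category at both times. SAP 2.3 limits by-visit summaries to scheduled visits. SAP 2.4 and Protocol 6.1.7 apply LOCF to efficacy variables, and Protocol 3.6.2 lists the MRI scan among these. None of these sections says how a final follow-up MRI is to be classified.

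**The concern.** The Month 12 comparison is there to show whether the MRI result at Month 6 still holds six months later. That needs a scan at Month 12. A subject who leaves in between has none, and the plan does not say that such a subject is left out.

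One route puts a scan taken perhaps one month after Visit 6 into the Month 12 row. The other puts the Month 6 rating there a second time. In both cases the table would show a Month 12 result that was never observed, and missing Month 12 data would not be visible.

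The analysis sets do not screen these subjects out. The per-protocol set asks only for ITT membership and completion of Visit 6 (Protocol 6.1.1.2, SAP 2.2.2), so a subject who stops after Month 6 belongs to both sets.

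**Working it through.** There is no planned figure to reproduce. Protocol 6.2 says that no formal sample size calculation was made, and no power is given for this test. The check is a reading of the rules, followed by simple arithmetic.

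**Timing.** The earliest final scan under 4.2.10 is about Month 6 + 1 = Month 7. The Visit 8 window opens one week before Month 12, at 12 − 7/30.44 = 11.77 months. The scan can therefore precede the window by 11.77 − 7 = 4.77 months.

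**What happens to a subject who stops between Months 7 and 11 and has a final scan.** Four readings are possible:

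1. The final follow-up is treated as Visit 8, following the shared schedule column or a ticked Month 12 box. The early rating becomes the Month 12 rating.
2. The final follow-up is kept separate but counts as an observation for LOCF. The early rating is carried to Month 12, with the same result as reading 1.
3. The final follow-up is excluded as unscheduled under SAP 2.3, and LOCF applies. The Month 6 rating is carried to Month 12, and the pair is unchanged by construction.
4. The final follow-up is excluded and LOCF is not applied to MRI. The subject drops out of the comparison.

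Only reading 4 leaves the subject out, and it needs an exception to LOCF that neither document states.

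**Effect on the percentages.** The planned JointStem group is 20 (Protocol 6.2). With 20 as the denominator, one subject is 1/20 = 5 percentage points. The documents do not give the number of early stoppers. For an assumed 1 to 4:

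| Stoppers | Share of 20 | Denominator if left out |
|---|---|---|
| 1 | 5% | 19 |
| 2 | 10% | 18 |
| 3 | 15% | 17 |
| 4 | 20% | 16 |

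The share is the most that the Month 12 percentage could move if every such rating differed from the unobserved Month 12 rating.

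**Effect on the test.** Bowker's statistic sums (n_ij − n_ji)² / (n_ij + n_ji) over the off-diagonal pairs of cells. A concordant pair lies on the diagonal and adds nothing, so reading 3 leaves the statistic as it is and changes only the percentages and the denominator. A discordant early pair, under readings 1 and 2, does enter.

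Two illustrations, with all k discordant pairs assumed to run in one direction:

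- Ratings collapsed to improvement yes/no, exact two-sided McNemar, p = 2 × 0.5^k: k = 5 gives 0.0625 and k = 6 gives 0.031.
- Three categories, asymptotic Bowker with 3 degrees of freedom, all k in one cell, so that the statistic equals k: k = 7 gives p = 0.072 and k = 8 gives p = 0.046.

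In each case one added discordant pair is enough to cross 5%. These show sensitivity; they are not forecasts.

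**The case against.** A reader might infer that the early scan can be recorded only as Month 12 and therefore enters the test as a Month 12 result. The documents do not go that far. SAP 6.2.3 names ratings at Month 6 and Month 12. Protocol 3.6.2 lists the final follow-up visit as an alternative to Visit 8, and the SAP does the same for the questionnaires. SAP 2.3 can be read to exclude a discontinuation visit. Appendix 9 also has no box for early termination or Month 24, although MRI is planned at both, so the missing box shows an incomplete form and does not prove miscoding. A site could leave both boxes blank or annotate the form. The SAP was built on electronic case report forms that are not in these documents, so the visit code in the database is unknown. All of this stands.

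A reader might also infer a bias towards a sustained effect. That is plausible for short intervals and true by construction for a carried-forward rating. But a subject who leaves because of worsening could be rated as progressed on an early scan. Since the documents do not settle which route applies, the direction is open. Nor do they say how many final scans there would be, because the site only tries to arrange the visit.

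Finally, this is one secondary within-group comparison in a study described as proof of concept. That limits the weight of the point. It does not answer it, because excluding the early scan under SAP 2.3 brings in LOCF and still fills the Month 12 cell.

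**Conclusion.** The point holds in this form: the plan does not fix how a final follow-up MRI is classified, and under the rules as written a subject with no Month 12 scan can be counted in the Month 12 versus Month 6 comparison by either of two routes. It rests on reading LOCF as covering the MRI rating, which is what the text says, since MRI is a listed efficacy variable and no exception is made.

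The size is up to 5 percentage points of the Month 12 table per subject, given 20 in the denominator. The total depends on an unknown number of early stoppers. Carried-forward pairs affect the percentages and the denominator but not Bowker's statistic; discordant early pairs affect both. The Month 6 co-primary MRI endpoint is untouched. The matter is worth correcting because the correction is small and the table would otherwise hide missing scans.

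**What to change.** 1. Add a dated final follow-up option to Appendix 9, as on Appendices 4 to 8, and give that visit its own code in the schedule and database. The questionnaire forms already have this choice and need no change.
2. In SAP 6.2.3, define a Month 12 MRI rating as one from a Visit 8 scan, within the Protocol's ± 1 week or a stated wider window.
3. State in the same place that LOCF does not apply to the MRI rating in this comparison. Without this sentence, excluding the early scan only replaces it with the Month 6 rating.
4. List final follow-up ratings separately with their interval from Month 6, and report how many JointStem subjects have no Month 12 MRI.
5. Reconcile the Schedule of Assessments and Protocol 3.6.2, which list the final follow-up MRI without the one-month condition, with Protocol 4.2.10. The two summaries omit the condition; they do not state an opposite rule.
6. Reconcile the item title in SAP 6.2.3, which names Months 9 and 12, with the schedule, which has no MRI at Month 9.

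The cost is one form change, a visit code and a few sentences. The statistical price is fewer Month 12 pairs, and a comparison confined to subjects who stayed to Month 12. The separate listing and the count of missing scans let a reader judge how selective that is.
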